3.5.2 Cycle 2 Assessments

During the 2nd week of treatment, the patient will have a complete blood count (CBC) with differential and platelet count. In phase I study, if grade 3 neutropenia is identified, repeat CBC with differential every 3 days until it improves to \leq grade 2. Patient may have CBC drawn at NIH lab or outside community lab.

During the 4th week of treatment (i.e. 28-day cycle), the patient will have the following assessments:

- Physical exam with vital signs, neurological exam, neurological function score and neurological examination (including documentation of the patient's Karnofsky Performance Status), mental status score. Weight is also included.
- A Gd-DPTA enhanced MRI, with DWI, ADC, SWI, FLAIR, perfusion, dynamic contrast enhanced and dynamic susceptibility contrast sequences should be performed.
- MD Anderson Symptom Inventory-Brain Tumor Module (MDASI-BT). If the MDASI-BT is completed by the patient for Natural History study within 14 days from the MRI assessment, it can be used but only if it was administered prior to informing patient of tumor imaging results.
- Toxicity monitoring

- A complete blood count (CBC) with differential and platelet count every two weeks. In phase I study, if grade 3 neutropenia is identified, repeat CBC with differential every 3 days until it improves to \leq grade 2.
- PT, PTT, INR, total protein, albumin, calcium, phosphorus, magnesium, glucose, BUN, creatinine, sodium, potassium, total bilirubin, alkaline phosphatase, LDH, SGPT (ALT), SGOT (AST) and a pregnancy test for women of childbearing potential
- 12-lead EKG.
- Response evaluation.

3.5.3 Subsequent cycles

For all subsequent odd-numbered cycles (i.e. cycle 3, 5, 7, 9, 11), patients will repeat assessments outlined in section **3.5.1**

For all subsequent even-numbered cycles (i.e. cycle 4, 6, 8, 10, 12), patients will repeat assessments outlined section **3.5.2**.

3.6 ASSESSMENTS AFTER COMPLETION OF STUDY THERAPY

Follow-Up Phase – Survival/Post-Disease Progression

Once a subject completes Phase II of study therapy or starts a new anti-cancer therapy, the subject moves into the survival follow up phase and should be contacted approximately within every 6 months to assess for survival status until death, withdrawal of consent, or the end of the study, whichever occurs first.

3.7 CCR SELF-ADMINISTERED STUDY DRUGS POLICY

All oral self-administered investigational agents will be properly accounted for, handled, and disposed in accordance with existing federal regulations and principles of Good Clinical Practice. All oral study drugs will be recorded in the patient diaries found in Appendix **15.7**. This will be used as a memory aide for subjects. A clinical research team maintains the primary source record.

3.8 STUDY CALENDAR

Procedure	Screening/ Baseline	Cycle 1				Cycle 2				Subsequent Odd numbered cycles		Subsequent Even numbered cycles		Off- study visit ⁸
		Wk 1	Wk 2*	Wk 3	Wk 4*	Wk 1	Wk 2*	Wk 3	Wk 4*	Wk 2*	Wk 4*	Wk 2*	Wk 4*	
Informed Consent	X													
Medical History	X													
Physical Exam ¹	X				X ¹				X ¹		X ¹		X ¹	X ¹
MDASI-BT	X								X				X ⁷	
ProCTCAE***	X	X	X	X	X	X	X	X	X	X	X	X	X	
GD-DPTA MRI of brain	X								X				X ⁶	
Hematology ²	X		X		X		X		X	X	X	X	X	X
Chemistry ³	X				X				X		X		X	X
PT/PTT/INR	X				X				X		X		X	
12-lead EKG	X				X				X				X	
Pregnancy Test ⁴	X				X				X		X		X	X
Tumor Pathology	X													
Paraffin Tissue block ⁵	X													
Response evaluation									X				X	
Research samples (PK, PG, neutrophil) ^{9,10}		X ^{9,10}												

1. Physical examination includes vital signs, neurological exam, neurological function score, Karnofsky performance score, mental status score. Height and weight are also included. **Height measured only at baseline.**
2. Includes CBC with differential and platelets. In phase I study, once grade 3 neutropenia is identified, CBC with differential will be tested every 3 days until it improves to \leq grade 2.
3. Includes: Total protein, albumin, Ca, Mg, P, glucose, BUN, creatinine, Na, K, total bilirubin, alkaline phosphatase, LDH, SGPT (ALT), SGOT (AST).
4. Only for women of childbearing potential as defined in section 15.2. To be performed before each new cycle of therapy.
5. If a tissue block is unavailable, unstained slides are acceptable.
6. Brain MRI w/wo contrast needs to be done every two cycles of treatment.
7. MDASI-BT questionnaire needs to be completed at imaging cycles within +/- 1week. (prior to imaging results having been discussed with the patient). If the MDASI-BT is completed by the patient for Natural History study (CC 16C0151) within 14 days from the MRI assessment, it can be used but only if it was administered prior to informing patient of tumor imaging results.
8. If patient does not return for 30-day safety visit, patient will be taken off study for reason listed in section 3.10.3 If patient does not return, physical exam and blood work is not mandatory.
9. On cycle 1 day -3, collect following samples from patients in the **Phase 1 cohort expansion only**: PK studies (1 6mL green sodium heparin tube at following timepoints-pre-dose, 1hr, 2hr, 4hr, 12hr, 24hr, 48hr, and 72hr post-oral dose); PG studies (1 purple tube EDTA, 6mL, pre-dose) and neutrophil analysis (2 additional purple top EDTA, 6mL each for CBC/diff and neutrophil marker; and 1 additional heparinized green top tube, 6 mL for plasma isolation for monitoring neutrophil activation markers) at following timepoints- pre-dose, 1hr, 2hr, 4hr, 12hr, 24hr, 48hr, and 72hr post-oral dose). All effort will be made to collect samples at prescribed time points; missed timepoints or collections outside the window will be documented but not constitute a deviation.
10. Research sample will be collected for PK/PG study from patients enrolled to the **Post-Interim Analysis cohort** at the following timepoints: pre-dose, 1hr, 2hr, 4hr, 24hr, and 48hr post-oral dose. This will avoid the requirement for inpatient admission. The neutrophil sample will not be collected.
*+/- 3 business days

** Allowance for scheduling changes: Brief interruption and delay in the 28-day cycle may occasionally be required due to travel delays, airport closure, inclement weather, family responsibilities, security alerts and government holidays, etc. This can also extend to complications of disease not attributable to disease progression or protocol therapy. These delays will not be considered protocol deviation. However, any interruption more than 14 calendar days will not be permitted.

*** on days 2, 8, 14, 21, and 28 (+/- 2 days). The ProCTCAE data will not be collected from patients enrolled to the post-interim analysis cohort.

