1.1.3 Exploratory Objectives

1.1.3.1 To obtain tumor tissues from initial occurrence and /or recurrence to detect *TP53*, *PTEN*, *IDH* mutation, *MYC* amplification status. The level of anti-apoptotic protein, such as Mcl-1 and XIAP, and caspase 3, cleaved PARP, c-Myc, CDK9 expression will be tested, if tissues are available at the time of recurrence.

1.1.3.2 To evaluate the imaging features by magnetic resonance imaging, including perfusion, before and during the treatment every two months.

1.1.3.3 To obtain blood samples after Zotiraciclib (TG02) dose on cycle 1, day -3 along with PK sample collection to analyze the effect of Zotiraciclib (TG02) on neutrophil count and functions.

1.1.3.4 To perform pharmacokinetic and pharmacogenomic studies of Zotiraciclib (TG02) once the MTD is determined in each cohort.

1.1.3.5 To explore the feasibility of Patient-Reported Outcomes Version of the Common Terminology Criteria for Adverse Events (PRO-CTCAE) in brain tumor patients receiving investigational cancer treatments.

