Patients will be enrolled to Arm 1 only to receive Zotiraciclib (at Dose level 0 and in combination of dd TMZ). TG02 dose is 200 mg/day orally on days 1, 12, 15, and 26 on a 28-days cycle, except for that the first dose of Zotiraciclib (TG02) will be given 3 days prior to Day1 in cycle 1. TMZ is administered at 125mg/m² daily on days 1-7 and 15-21 orally on a 28-days cycle.

3.2.2 Phase II treatment:

The combination treatment selected from phase I (with better PFS4) will be tested against the TMZ alone with the same dosing schedule as it is in the combination arm. Patients will be randomized on a 1:1 basis between two competing treatment arms: TMZ + Zotiraciclib (TG02) versus TMZ alone using a Bayesian phase II trial design. The details of the design are provided in Section 8.

The dosage for the combination arm is derived from the MTD of the combination determined in the phase I component of the study. The treatment schedule will be identical to that described above in the phase I component, with each cycle comprising 28 days.

Patients will continue treatment until tumor progression or unacceptable toxicity occurs or completion of 12 cycles of treatment. At progression, patients randomized to the control arm (TMZ alone) will be offered the opportunity to continue TMZ and the additional treatment with Zotiraciclib (TG02). After administration of 12 cycles of treatment, patients may stay on the study treatment, if there is evidence of clinical benefit based on treating physician's discretion.

If patient vomits Zotiraciclib (TG02), do not re-administer.

3.3 DOSE MODIFICATION/DELAYS:

If an adverse event occurs wherein both TMZ and Zotiraciclib (TG02) would require dose de-escalation, the Principal Investigator shall have the discretion of first dose reducing one of the 2 study drugs with the consideration of previously known drug toxicities/side effects in an effort to further define attribution.

Table 8: Start of Each Cycle for both TMZ and Zotiraciclib (TG02)		
Temozolomide and Zotiraciclib (TG02)		
Hematologic*	ANC $\geq 1.5 \times 10^9/L$ and PLT $\geq 100 \times 10^9/L$	No dose modification
	ANC $< 1.5 \times 10^9/L$ and/or Platelet count $< 100 \times 10^9/L$	Delay up to 4 weeks until ANC $\geq 1.5 \times 10^9/L$ and PLT $\geq 100 \times 10^9/L$. If unresolved after 4 weeks, then stop. If resolved, dose delay/reductions based on Table 9.
Non-Hematologic	Grade 1 or less	No dose modification

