3.3.1.1 Delay

For treatment on day 1 of each cycle (within the prior 72 hours), ANC $\geq 1.5 \times 10^9/L$, platelet count $\geq 100 \times 10^9/L$ and all grade 2 -3 non-hematologic AEs (except nausea and vomiting) must have resolved (to grade ≤ 1). For grade 4, discontinue treatment. For the purposes of this study, any clinically insignificant Grade 2 or 3 electrolyte abnormalities with attribution of unlikely related to or unrelated to study medications, will not require holding or dose-reducing study medications.

If AEs persist, treatment may be delayed by 1 week for up to 4 consecutive weeks. If, after 4 weeks of delay, all AEs have still not resolved to grade 1 or less: then any further treatment with temozolomide should be stopped, as summarized in Table 8 and Table 11.

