6.3.4 Response Criteria

Response and progression will be evaluated in this study using the new proposed criteria Response Assessment in Neuro-Oncology Criteria (RANO) (see Appendix 15.5).[49]

Complete response: Requires all of the following:

- Complete disappearance of all enhancing measurable and non-measurable disease sustained for at least 4 weeks.
- No new lesions and stable or improved non-enhancing lesions (T2/FLAIR)
- Patient off steroids or on physiologic replacement only.
- Stable or improved clinically.

Partial response: Requires all of following:

- ≥ 50 % decrease compared to baseline (prior to treatment) in the sum of the products of perpendicular diameters of all measurable enhancing lesions sustained for at least 4 weeks;
- No new lesions and stable or improved non-enhancing lesions (T2/FLAIR).
- Patients off steroids or on physiologic replacement only.

- Stable or improved clinically.

Stable disease: Requires all of the following:

- Not complete response, partial response or progression.
- Stable non-enhancing lesions (T2/FLAIR).
- Patient on same or lower dose of steroids compared to baseline scan.

Progression: Requires any of the following:

- ≥ 25 % increase compared to baseline in the sum of the products of perpendicular diameters of enhancing lesions compared with the smallest measurement obtained either at baseline or best response with the patient on stable or increasing doses of steroids.
- Significant increase in T2/FLAIR non-enhancing lesions with the patient on stable or increasing doses of steroids (not caused by comorbid events e.g. Radiation therapy, demyelination, ischemic injury, infection, seizures, medication adverse events or changes in corticosteroid dose).
- Any new lesions.
- Failure to return for evaluation as a result of death or deteriorating condition or clear progression of non-measurable disease.

6.3.5 Patients will undergo response evaluations every 2 months.

- RANO criteria will be used to determine response and progression (includes CR, PR, SD and PD) **15.5**.
- Neurological exam.
- Performance status by Karnofsky Performance Status.

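### MRI dates follow treatment cycles that can slip while PFS runs on calendar time from registration, and PFS4 has no day count, so unequal delays can shift PFS4 and PFS between doses or arms.

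*Combined protocol and SAP*

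**What the plan says.** **Scan timing by cycle.** Section 3.8, footnote 6: "Brain MRI w/wo contrast needs to be done every two cycles of treatment". Section 3.5.2 puts the MRI and the response evaluation in week 4 of cycle 2: "During the 4th week of treatment (i.e. 28-day cycle), the patient will have the following assessments". Section 3.5.3 carries this forward: "For all subsequent even-numbered cycles (i.e. cycle 4, 6, 8, 10, 12), patients will repeat assessments outlined section" 3.5.2.

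**Scan timing by calendar.** The imaging objective (1.1.3.2) has MRI "before and during the treatment every two months", and Section 6.3.5 states: "Patients will undergo response evaluations every 2 months".

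**Cycles can slip.** Table 8 (Section 3.3), for low counts at a cycle start: "Delay up to 4 weeks until ANC" and platelets recover. Section 3.3.1.1: "treatment may be delayed by 1 week for up to 4 consecutive weeks". The note under the study calendar adds: "Brief interruption and delay in the 28-day cycle may occasionally be required due to travel delays" and similar causes, with a limit of 14 calendar days. Section 3.3.1 lets zotiraciclib continue while temozolomide is held, and no text says which drug's start then defines the cycle.

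**The endpoint runs on the calendar.** Section 6.3.8 measures PFS from registration. PFS4 appears in Sections 3.1.1 and 10.1 only as PFS at 4 months, with no day count and no rule for a scan that falls late. PFS4 chose the TMZ schedule. It will also choose between the MTD and the next lower dose on a 5% difference (10.1). PFS is the Phase II primary endpoint (10.2).

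**The concern.** Progression seen only on imaging is dated by the scan. When a delayed cycle delays the scan, the event date moves later even though the tumour has not changed. The effect is sharpest for PFS4, because the on-time cycle-4 scan falls just before month 4. If the scan crosses that day, the patient's 4-month status rests on the cycle-2 scan, about two months earlier.

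Delays shared equally shift all groups together. Unequal delays produce a difference where none exists. Toxicity is the main stated reason for delay, and the comparisons are between two doses and between a combination and temozolomide alone, so unequal delays are plausible. The Phase II dose and the Phase II primary comparison are what could be affected.

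**Working it through.** **1. Scan day, counted from registration.** Treatment starts 0-7 days after registration (2.3). The first zotiraciclib dose is 3 days before cycle 1 day 1 (Table 7 footnote), so day 1 is registration + 3 to 10. Week 4 of cycle 4 is days 22-28 after three 28-day cycles: 84 + 21 = 105 to 84 + 27 = 111 days after day 1.
- On time: 3 + 105 = 108 to 10 + 111 = 121.
- One 7-day delay: 115-128.
- One 14-day delay: 122-135.
- One 28-day delay: 136-149.

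Four months is 4 x 30.4375 = 121.75 days. The visit tolerance of 3 business days comes on top.

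**2. How often the scan crosses the cut.** Assume each start of cycles 2-4 slips one week with probability s, with start day and scan day spread evenly (8 x 7 = 56 combinations). With no slip, no scan passes day 121.75. With one slip, 28/56 = 50% do. With two or more, all do. So the share is 0.5 x 3s(1-s)^2 + [1 - (1-s)^3 - 3s(1-s)^2]:
- s = 10%: 0.1215 + 0.028 = 15%
- s = 25%: 0.211 + 0.156 = 37%
- s = 50%: 0.1875 + 0.500 = 69%

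**3. Measured PFS4, cut at day 122.** Assume exponential PFS with median 3 months in everyone (the control figure in 10.2). The true value is 0.5^(121.75/91.3) = 39.7%. Simulating with progression found only at scans gives the middle column. If a share c is found clinically at its true time, measured PFS4 = (1-c) x that value + c x 39.7%.

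| Slips per cycle start | c = 0 | c = 50% |
|---|---|---|
| 0% | 42% | 41% |
| 10% | 45% | 42% |
| 25% | 49% | 44% |
| 50% | 55% | 47% |

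The false gap is about 2-4 points for 10% versus 25% slips and about 3-6 points for 25% versus 50%. Placing every scan on day 28 of the cycle gives 2.2-5.7 and 2.6-5.7 points.

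**4. If 4 months means day 112 (four cycles).** The true value is 0.5^(112/91.3) = 42.7%. Of the 56 on-time combinations, 15 fall on or before day 112, so 41/56 = 73% of on-time scans come too late. On-time PFS4 then reads about 50-58%. The false gap between groups is only about 2 points or less, but the level is well off. The missing day count therefore matters even without delays.

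**5. Effect on the dose rule.** Read 5% as 5 percentage points. With 18 patients at the MTD and n at level 0, the higher dose is chosen with probability equal to the sum of Bin(a; 18, p1) x Bin(b; n, p0) over all a/18 - b/n >= 0.05. The plan adds 12 patients at level 0 and does not say how many were already there, so take n = 12-18.
- No true difference and no delay imbalance (p = 0.41 in both): 35-43% across n, and about 38% at n = 15.
- n = 15, MTD dose slips more: 43-47% (25% versus 10% slips) and 44-52% (50% versus 25%).
- n = 15, lower dose slips more, c = 0: 29% and 26% respectively.

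**6. Against noise.** The SD of the PFS4 difference at n = 15 is sqrt[0.41 x 0.59 x (1/18 + 1/15)] = 17 points.

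**7. Interim schedule choice.** The observed difference is 38 - 25 = 13 points. The plan's threshold is 10% of the average, 0.10 x 31.5 = 3.2 points. Taking off the largest gap in step 3, 13 - 6 = 7, still above it.

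**8. Phase II log-rank.** Simulated with 40 per arm, 4 patients a month, 12 months' follow-up and no true difference. The critical value z = -1.96 is assumed because no alpha is stated. One-sided false rejection is 3.6-5.3% with 50% versus 25% slips, against about 2.5-3% with scans fixed every 8 weeks.

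**The case against.** **The operative text is mostly cycle-based.** Sections 3.5.2 and 3.5.3 and footnotes 6 and 7 all count cycles, and two months can be read as shorthand for two 28-day cycles. This is largely right. It settles the wording in favour of cycles, but that is the reading under which scans slip. The documents still do not say what happens to the scan after a delay.

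**The harm rests on assumed delay contrasts.** No delay rates are given. Both doses in the Phase II dose choice start the same temozolomide. Section 3.3.2 attributes prolonged myelotoxicity mainly to temozolomide, and Section 1.2.7 reports neutropenia after zotiraciclib usually recovering in 24-48 hours. Large week-long differences between 200 and 250 mg are therefore less likely, though non-hematologic delays could differ. This stands and limits the point to a cheap improvement. In the dose rule, the size of the level-0 cohort alone moves the unbiased baseline by about 8 points (35-43%).

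**Stronger readings that the documents do not support.**
- A reader might infer that the plan favours the higher dose or the combination. The direction depends on who is delayed more, which is unknown.
- A reader might infer, because Section 10.1 says only AE and PFS4 will be recorded for the added cohort, that its scan dates could be lost. The study calendar does not exempt this cohort from MRI, Section 6.3.3 requires objective status to be recorded at each evaluation, and the pill diaries carry dates by cycle day.
- A reader might doubt the choice of the dose-dense schedule. Step 7 of the working shows that gaps of this size do not overturn it.

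**Conclusion.** The point holds as a design weakness. As written, scan dates move with treatment delays, the endpoint clock does not, and PFS4 has no day count. Unequal delays can then create a false PFS4 gap comparable to the 5% dose-selection margin under some delay patterns, and a small inflation of the Phase II log-rank error. The sizes rest on exponential PFS with a 3-month median, one-week slips, 0-50% clinical detection and assumed delay rates. Zero clinical detection is an upper bound, because Section 6.3.4 counts death and deterioration as progression. No figure stated in the plan is wrong on this account. The case for acting is that the bias is systematic and cheap to avoid.

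**What to change.** **Phase II.** Amend 3.5.2, 3.5.3, footnote 6 and 6.3.5 so that MRI and RANO assessment fall every 8 weeks from registration, +/- 7 days, identically in both arms and regardless of cycle delays or drug holds. Keep MDASI-BT with the scan. The week-16 window then closes on day 112 + 7 = 119 and the week-24 window on day 168 + 7 = 175, before 4 months (122) and 6 months (183). The timing of the repeat scan in 3.10.1, now tied to one further cycle, must be reconciled with this schedule without changing how long treatment may continue.

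*Cost:* calendar wording and about the same number of scans. For delayed patients the scan may not coincide with the cycle visit, so some need an extra visit. *Limit:* the change does not reach patients who stop treatment before progression, for whom no later MRI is scheduled.

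**Dose choice.** Do not re-time scans for the level-0 cohort alone, because different scan rules at the two doses would themselves create a gap. Before that cohort is read out:
- define PFS4 in 10.1 as Kaplan-Meier PFS at day 122 from registration, applied identically to both doses;
- state that this definition was set after the Arm 1 interim result was known;
- report actual scan days and cycle delays by dose, since a common day count does not by itself remove the scan-timing effect;
- add an interval-censored PFS4 estimate for both doses as a supportive sensitivity analysis.

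*Cost:* a short paragraph in 10.1, applying the definition to MTD data already collected, and one extra analysis. No new scans.

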3.9 SURGICAL GUIDELINES

If neurosurgical management is required for reasons not due to tumor progression, these procedures must be documented, including the indications for surgery, the surgical operative note and pathology report. Study treatment may be resumed per discretion of the PI.

3.10 CRITERIA FOR REMOVAL FROM PROTOCOL THERAPY AND OFF STUDY CRITERIA

3.10.1 Criteria for Removal from Protocol Therapy

- After administration of 12 cycles of treatment, unless there is clear evidence of clinical benefit to justify continuation of treatment based on treating physician's opinion.
- Progressive disease if patient not eligible for or refuses crossover or progressive disease * after crossover to TMZ+ Zotiraciclib (TG02)
- The patient may withdraw from the study at any time for any reason
- Unacceptable Toxicity as defined in section **3.3**
- Investigator discretion
- Treatment related adverse events not resolved within a 4-weeks rest period or requiring more than two dose de-escalations of any drug whichever is earlier.
- Pregnancy

* Delayed imaging responses have been observed in some patients who received protocol treatment. If a patient is clinically stable or clinically improved, even while MRI showed >25% increase in tumor size, the patient may continue on study treatment per P.I. discretion for one additional cycle, at which time a repeat scan will be done. If tumor size continues to increase, disease progression will be dated back to the date of prior MRI.

